2.3.2 KNOWN POTENTIAL BENEFITS

Potential Benefits of the Proposed Research to Human Subjects and Others

Participants. Participants have the potential to benefit from improved CVD risk awareness and health behaviors (e.g., nutrition, physical activity, coping strategies, self-efficacy). They may receive some psychological benefit from stress management sessions and learning coping skills such as problem-solving. Participants may also benefit from the study by decreasing their biologic CVD risk (i.e., blood pressure, arterial stiffness, weight, waist circumference).

Others/Community. The proposed research has potential public health benefits because Hispanic/Latinos are the largest ethnic minority in the United States. Progress regarding CVD risk among perimenopausal Latinas may lead to significant improvement in the overall CVD burden in the US.

2.3.3 ASSESSMENT OF POTENTIAL RISKS AND BENEFITS

See 2.3.1 above for assessment of potential risks and benefits

3 OBJECTIVES AND ENDPOINTS

Primary Objective: To examine the feasibility and initial efficacy of the multi-component behavioral intervention to reduce biologic CVD risk from Time 1 (baseline) to each of Time 2 (6 months) and Time 3 (12 months).

Secondary Objective: To evaluate the initial efficacy of the intervention to improve health behaviors, adiposity, inflammatory and stress biomarkers, and vasomotor symptoms from Time 1 (baseline) to each of Time 2 (6 months) and Time 3 (12 months).

Primary Outcomes:

- Systolic and diastolic blood pressure
- Carotid-femoral pulse wave velocity
- Total cholesterol
- High-density lipoprotein
- Low-density lipoprotein
- Triglycerides
- Fasting blood glucose
- Enrollment and retention rates
- Intervention attendance
- Participant satisfaction with the intervention and study protocol

Secondary Outcomes:

- Health behaviors (nutrition, physical activity, sleep)
- Self-efficacy (eating and exercise)
- Adiposity (weight, body mass index, waist circumference)
- High-sensitivity C-reactive protein
- Hair cortisol

Other Outcomes:

- Vasomotor symptoms

4 STUDY DESIGN

4.1 OVERALL DESIGN

This study will use a cluster randomized repeated measures study design with two groups to evaluate the feasibility and initial efficacy of the intervention with 80 perimenopausal Latinas. The intervention group (n=40) will receive a 3-phased intervention. In Phase I (Intensive Intervention), bilingual community health workers will meet with women in small groups to deliver 12 weekly (3 months) 2-hour sessions including education, group physical activity, stress management, and coping skills training. Phase II (Continued Support) consists of 3 monthly 1-hour sessions led by community health workers to problem-solve issues related to nutrition and exercise, stress management, and to provide feedback and support. During Phase III (Follow-up), participants are expected to maintain skills on their own for 6 months. Data will be collected at baseline (Time 1), completion of Phase II (Time 2, 6 months after baseline), and after completion of 6 months on their own (Time 3, 12 months after baseline). Data in the wait-list control group (n=40) will be collected at the same time intervals as the intervention group. After Time 3 data collection, they will be offered the Intensive Intervention (12 weekly sessions). Both groups will receive reminders a week prior to each data collection visit and a monthly "thank you" card for their continued participation.

Data will be collected at Time 1 (0 months [baseline]), Time 2 (6 months [completion of the intervention]) and Time 3 (12 months [after 6 months with no contact from the study staff]). Time 2 data will determine the magnitude of the intervention effects after the intensive intervention and continued support; Time 3 data collection will test initial efficacy after participants have had sufficient time to implement their new nutrition, physical activity, and coping skills on their own. We will assess feasibility using questionnaires at Time 3, as well as process evaluations and attendance logs. We chose these times because 6-to-12 months after completion of an intervention is a standard interval for follow-up in behavioral interventions during perimenopause [34].

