2 INTRODUCTION

2.1 STUDY RATIONALE

Background: CVD remains the leading cause of death for women globally. In women, risk of CVD increases substantially during perimenopause. Latinas have a significantly worse CVD risk factor profile than non-Hispanic White women, attributable to several factors including lower socioeconomic position, interpersonal violence, discrimination, and stress. These factors are related to CVD through their influence on health behaviors as well as potential mechanisms involving inflammatory and neuroendocrine pathways. Despite their increased risk, however, perimenopausal Latinas remain underrepresented in CVD research.

Methods: This study is guided by the National Institute of Minority Health and Health Disparities (NIMHD) Framework, which considers the interplay between sociocultural environment, built environment, behavioral influences, and biological influences on health. Using a cluster randomized two-group, repeated measures experimental design, the goal of this study is to investigate the feasibility and initial efficacy a 12-month intervention integrating evidence-based education and coping skills training with physical activity and stress management. The intervention has three phases: 12 weekly sessions (Phase I: education, physical activity, stress management, coping skills training) followed by 3 monthly sessions of continued support (Phase II); and finally 6 months of skill maintenance on their own (Phase III). Measurement visits will occur at baseline, 6, and 12 months. We will conduct in-depth exit interviews with participants to assess barriers and facilitators to recruitment and enrollment, delivery of the intervention, fidelity, and suitability of assessment procedures. We will partner with local churches and community centers in two counties to recruit participants and deliver the intervention. Data will be collected at Time 1 (0 months [baseline]) to Time 2 (6 months [completion of the intervention]) and Time 1 to Time 3 (12 months [after 6 months with no contact from the study staff]). Data collected will include blood pressure, lipid profile, blood glucose, and arterial stiffness. Secondary outcomes will include health behaviors and self-efficacy, adiposity, inflammatory and stress biomarkers, and vasomotor symptoms.

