To strengthen retention, our intervention sessions will be interactive, with culturally-tailored content developed to engage and sustain participants' interest (*Su Corazón, Su Vida* curriculum and coping skill training). Women who miss a learning session will be offered an opportunity to review the weekly class content over the phone, and will be reminded when the next class will be held. We will provide women with handouts including tips, a list of resources, recipes, and illustrations in Spanish on how to improve their nutrition, physical activity, and sleep. We will ask participants for phone numbers of family members and permission to call them if we cannot contact them. We will be flexible in scheduling enrollment and data collection appointments and send thank you cards. We will remind participants of their data collection visits one week before and confirm the day before the appointment. Participants in both groups will receive \$35 after the baseline visit, \$40 after the 6-month visit, and \$45 after the 12-month data collection. These approaches have been successful in prior studies with Latinas, with <20% attrition [43]. We will make every effort to keep our attrition lower than 20%; if attrition exceeds 20%, we will contact the participants to ask why they stopped coming and develop strategies to assist them to continue in the study if they wish. We will also meet with our Community Advisory Board to develop and implement strategies to improve retention.

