6.2 FIDELITY

6.2.1 INTERVENTIONIST TRAINING AND TRACKING

Fidelity of the Intervention

We have structured the fidelity of the intervention using the NIH five category Treatment Fidelity Framework [44]. For category one, **treatment design**, the intervention and control group condition is clearly defined and participants will receive the same duration of contact over time. The CHWs will have experience teaching health interventions, and the theoretical model is clearly articulated. For category two, **training**, The bilingual interventionists will be trained by the PI using a standardized manual and teach back the intervention to the PI. For category three, **delivery**, the bilingual project coordinator will observe two randomly selected sessions per month using a checklist to score delivery based on pre-identified content. We define fidelity as delivering >80% of the protocol content. If drift occurs, the PI will retrain CHWs until the protocol is followed consistently. CHWs will collect data on attendance, reasons for absence, and make-up learning sessions provided. For category four, **receipt**, interventionists will ask questions and generate discussion during each learning sessions to assess the degree to which participants understand the content and participants will be asked to set a goal based on the information reviewed during the learning session. CHWs will evaluate category five, **enactment**, during the 3 monthly continued support sessions by discussing changes in diet, physical activity, number of steps taken per day, and stress management; RAs will also assess enactment during exit interviews at Time 3 with participants.

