Subject Accrual and Compliance with Inclusion/Exclusion. All data from participants screened for the study will be entered into the REDCap electronic study database. Designated research staff will collect, gather, and enter required data (written informed consent, Health Insurance Portability and Accountability Act (HIPAA) authorization, medical history and demographics) onto study data forms. Screened patients who do not meet study eligibility will have specific screening data entered into the study database. The collected data will be helpful in examining the patient population and feasibility of enrollment criteria and will include gender, age, race and reason for exclusion. All dates will be shifted and other Personal Health Information (PHI) will be removed from the study database upon study completion.

Participant Compliance to the Intervention. Data on compliance to the intervention will be collected weekly by the senior RA and reviewed quarterly by the Co-Mentors, scientific advisors, the Senior RA, Safety Officer, and PI. Compliance on the part of participants will be evaluated by attendance and process evaluation as outlined in the study. If intervention attendance drops below 80%, participants who have stopped coming will be called to ask for feedback. Using information gained from these phone interviews, the PI will schedule a meeting with the Co-mentors, scientific advisors, and the Safety Officer to discuss methods for improving compliance.

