9.4 STATISTICAL ANALYSES

9.4.1 GENERAL APPROACH

Aim 1. Using descriptive statistics (e.g., frequency, percentage, means, SDs), we will summarize enrollment and retention rates, and proportion of intervention sessions the participants attended. We will measure fidelity of the intervention ($\geq 80\%$ attendance; delivery of $>80\%$ of content) using the process evaluation guide, and assess participant satisfaction with the study and the intervention using the exit interview.

Aim 2. We will use an intent-to-treat approach. Because random assignment is by group and not individually, we will examine potential systematic differences closely between the two groups, comparing baseline characteristics using the Student's t-test or Mann-Whitney test for continuous variables and Chi-square or Fisher's exact test for categorical variables. We will assess change in primary and secondary outcomes in the intervention and control group using the Student's t-test or Mann-Whitney test for continuous variables and Chi-square or Fisher's exact test for categorical variables.

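### Participant satisfaction, a primary feasibility outcome, is measured only at the 12-month exit interview, so women lost before then give no satisfaction data

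*Combined protocol and SAP*

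**What the plan says.** **Status of the outcome.** Section 3 lists among the primary outcomes "Participant satisfaction with the intervention and study protocol".

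**Instrument.** In section 9.4.1 the analysis of Aim 1 will "assess participant satisfaction with the study and the intervention using the exit interview". No other instrument is named for satisfaction.

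**Timing.** Section 4.1 says "We will assess feasibility using questionnaires at Time 3", and the same sentence adds process evaluations and attendance logs. The schedule tables in sections 1.3 and 8.1 each mark the exit interview once, at 12 months. Section 6.2.1 confirms the timing: "RAs will also assess enactment during exit interviews at Time 3 with participants".

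**Contact with women who leave or stop attending.**
- Section 5.5: "if attrition exceeds 20%, we will contact the participants to ask why they stopped coming".
- Section 8.3.3.2: "If intervention attendance drops below 80%, participants who have stopped coming will be called to ask for feedback".
- Section 7.2 requires the reason for any discontinuation or withdrawal to be recorded, at any attrition rate.
- Section 7.3 requires contact attempts after a missed visit (three telephone calls where possible) before a woman is declared lost.
- Section 6.2.1 has the community health workers record why women were absent.
- Section 8.3.4 adds semi-annual qualitative reports covering barriers, acceptability and user feedback, drawn from phone calls and end-of-study surveys.

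The documents give no satisfaction item at Time 2 or at withdrawal, and no rule for missing satisfaction data.

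**The concern.** A pilot is meant to show what would go wrong in the larger trial, and section 8.3.4 says its findings will inform that trial's design. Satisfaction is one of the outcomes that carries this information. As planned, it comes only from women still in contact at month 12. A woman who left because the classes or the study visits did not suit her is the one whose rating would be most useful, and she is not asked for one.

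Timing is a second, smaller weakness. Classes end at Time 2 and the interview is at Time 3, so even retained women first rate the intervention after six months without contact from staff. Their answers may reflect recall as much as experience.

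If the main-trial team reads a high satisfaction rate with no denominator, it may keep features of the intervention or the visit schedule that drove some women away.

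**Working it through.** The plan states no satisfaction figure, target or go/no-go threshold, so there is no figure to reproduce. The check has two parts.

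**1. Do the other contacts measure satisfaction?**

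| Source | When it applies | What it yields |
|---|---|---|
| Exit interview (9.4.1, 6.2.1) | Time 3 only | Satisfaction |
| Withdrawal reason (7.2) | Any withdrawal | A reason |
| Missed-visit contact (7.3) | Any missed visit | Whether she wishes to, or should, continue |
| Absence reasons (6.2.1) | Missed classes | A reason |
| Attrition calls (5.5) | Attrition above 20% | Why she stopped |
| Attendance calls (8.3.3.2) | Attendance below 80% | Feedback, to improve compliance |
| Semi-annual reports (8.3.4) | Twice a year | Barriers, acceptability and feedback, from phone calls that are not defined and surveys returned at the end of study |

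Only the first row is a satisfaction measure. The attendance trigger cannot apply to wait-list women, who have no classes before Time 3, or to losses in Phase III, when classes are over.

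**2. How far could the rate among interviewed women be from the rate among all enrolled?**

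Inputs:
- Loss before Time 3, *d*: sections 5.5 and 9.2 expect less than 20%; 20% is used as the upper planning value.
- Group size: 40 per group, 80 in total (section 4.1).
- Satisfaction among those interviewed, *p*c: 90%, an assumption.
- Satisfaction among those lost, *p*d: unknown, from 0 to 1.

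Women without an interview: 0.20 × 40 = 8 in the intervention group; 0.20 × 80 = 16 overall. The base of 40 applies to satisfaction with the intervention, because wait-list women have not received it by Time 3. The base of 80 applies to satisfaction with the study protocol.

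Rate among all enrolled = (1 − *d*) × *p*c + *d* × *p*d. 
Error in the reported rate = *d* × (*p*c − *p*d).

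Bounds at *d* = 0.20 and *p*c = 0.90:
- No lost woman satisfied: 0.80 × 0.90 = 0.72, so the reported rate is 18 points too high.
- Every lost woman satisfied: 0.72 + 0.20 = 0.92, so the reported rate is 2 points too low.

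Between the bounds, under assumed satisfaction among those lost:

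| *p*d | Error = 0.20 × (0.90 − *p*d) |
|---|---|
| 30% | 12 points |
| 50% | 8 points |
| 60% | 6 points |
| 70% | 4 points |
| 90% | 0 |

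Sensitivity to the other inputs:
- *d* = 0.10, *p*c = 0.90: 0.90 × 0.90 = 0.81, to 0.81 + 0.10 = 0.91.
- *d* = 0.20, *p*c = 0.80: 0.80 × 0.80 = 0.64, to 0.64 + 0.20 = 0.84.

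The width of the range equals the proportion lost.

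**The case against.** The strongest reply is that the plan does not ignore women who leave. Withdrawal reasons and missed-visit contacts apply at any attrition rate. The attendance trigger is also more sensitive than it looks: if 8 of 40 intervention women stopped at the outset, the other 32 would need perfect attendance to hold the group at 32/40 = 80%. Early dropout would therefore probably prompt calls. The interviews are in-depth and Aim 1 is summarised descriptively, so a percentage satisfied is a scale that the plan itself does not define. Asking at the end is also defensible, since the outcome includes the study protocol, which runs to month 12.

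Much of this stands, and it rules out several stronger readings that a reader might infer:

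- *That barriers, too, are measured only at Time 3.* Section 2.1 does say "We will conduct in-depth exit interviews with participants to assess barriers and facilitators to recruitment and enrollment", but sections 5.5, 6.2.1, 7.2, 8.3.3.2 and 8.3.4 supply other sources.
- *That 16 of 80 women could leave without being asked anything.* Sections 7.2 and 7.3 have no threshold. What these women are not asked is a satisfaction question.
- *That the interview reaches only completers.* Section 4.4 defines completion as all three data collections. A woman who stopped classes or missed Time 2 can still be interviewed at Time 3.
- *That the result is certainly biased upward.* Some exits have nothing to do with dissatisfaction; section 8.3.9, for example, withdraws women who become pregnant. The bounds above allow a small error in the other direction.

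The reply does not supply a satisfaction rating from anyone lost before month 12.

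**Conclusion.** The point holds for satisfaction. Followed exactly, the plan yields a satisfaction result from women seen at Time 3 only, with no provision for those lost earlier. It is likely too favourable if lost women are less satisfied than retained women. That is a plausible assumption, but the documents do not establish it.

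The 72% to 92% range is illustrative. It rests on 20% loss, which is the top of the plan's own expectation, and on an assumed 90% among those interviewed; at 10% loss it narrows to 81% to 91%. The six-month gap after the last class takes Phase II as the three monthly sessions of sections 4.1 and 6.1.1.

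Retention and attendance, also primary feasibility outcomes, count women who leave and are not affected. The efficacy analysis is not affected either. This is an inexpensive improvement to one primary outcome, not a flaw that undermines the pilot.

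**What to change.** 1. Add a few satisfaction items for intervention women at the existing Time 2 visit. This covers women lost between months 6 and 12 and removes most of the recall gap.
2. Ask the same items when any woman withdraws, or when she is reached during the contact attempts that section 7.3 already requires, whatever the attrition or attendance rate. Wait-list women would answer only the items on the study protocol.
3. In section 9.4.1, state that satisfaction will be reported with the number interviewed against the number enrolled in each group, and with best- and worst-case bounds for non-responders.

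Some women will remain unreachable, which is why the bounds are needed as well as the calls.

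The cost is a few added items at one visit and a small number of short calls by existing staff: at 20% loss, at most 16 women, fewer of whom will be reached. The design, the sample size and the efficacy analysis do not change.

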4.2 SCIENTIFIC RATIONALE FOR STUDY DESIGN

Preliminary studies have demonstrated that perimenopause is an important time to implement behavioral interventions for the prevention of CVD. While behavioral interventions have been shown to increase CVD risk awareness and knowledge of heart-healthy behaviors (e.g., diet and exercise) among Hispanics/Latinos [31,32], most interventions among Latinas have been education only with either a short follow-up (<6 months) [31] or no assessment of biologic CVD risk [33]. Additionally, although studies among non-Hispanic White and Black women have shown that dietary and physical activity interventions can slow the progression of subclinical atherosclerosis during perimenopause [35], no such interventions have focused on perimenopausal Latinas. Our study will address important limitations of prior interventions. We will pilot test a novel multi-component behavioral intervention integrating evidence-based education - SCSV curriculum [36] - with coping skills training developed and tested by Co-Investigator [name] [37], physical activity sessions, and stress management. Thus, this is a

novel multi-component intervention to reduce biologic CVD risk (blood pressure, arterial stiffness, lipids, blood glucose) and to improve health behaviors (nutrition, physical activity, sleep, coping strategies, self-efficacy, stress management) among perimenopausal Latinas.

4.3 JUSTIFICATION FOR INTERVENTION

Risk of CVD increases substantially during perimenopause. Perimenopausal Latinas remain considerably less likely than non-Hispanic White women to meet physical activity and dietary guidelines, or be aware that CVD is the leading cause of death among women. In North Carolina and throughout the US Latinas often live in a sociocultural environment of poverty, have limited English proficiency, and face social isolation and discrimination [37]. Latinas often reside in built environments that may further contribute to CVD risk due to limited access to affordable healthy food options and safe public spaces for physical activities [38]. We will collect data on the sociocultural and built environment to tailor the intervention, and intervene on the behavioral influences of cardiovascular health (i.e., nutrition, physical activity, sleep, stress management, coping strategies and self-efficacy) to decrease biologic CVD risk among perimenopausal Latinas. Community health worker-led behavioral interventions among Latinos have been successful in improving health behaviors [31,32], although reduction of biologic CVD risk has been inconsistent [31,39]. Importantly, prior interventions have not targeted perimenopausal Latinas specifically or examined arterial stiffness, an independent predictor of CVD events [29]. Furthermore, these interventions have not incorporated physical activity, stress management, and coping strategies, essential components to reduce CVD risk among perimenopausal Latinas. To address these deficits, this 12-month multi-component behavioral intervention integrates evidence-based education and coping skills training with physical activity and stress management to 1) reduce biologic CVD risk, including arterial stiffness; and 2) improve secondary outcomes of health behaviors, adiposity, inflammatory and stress biomarkers, and vasomotor symptoms.

